Protocol Title

Post stroke walking kinematics using the Honda Walking Assist (HWA) robotic exoskeleton

Principle Investigator: [name] PhD, PT, NCS

Department of Physical Therapy

College of St. Scholastica [name] [contact] [contact] [contact]

Co-Investigators: [name] PhD, PT

Department of Physical Therapy

College of St. Scholastica [name] [contact] [contact] [contact]

[name] PT, DPT

Department of Physical Therapy

College of St. Scholastica [name] [contact] [contact]

[contact]

Study Device: Honda Walking Assist designed and developed by Honda R & D

Americas, Inc.

[figure not shown]
Funding Source: Honda R & D Americas, Inc.

Initial Version: 10-2-2018

10-8-2018 Revised by AB

Study Summary:

Title	Post stroke walking kinematics using the Honda Walking	
	Assist (HWA) robotic exoskeleton	
Short Title	Post stroke walking kinematics using the HWA robotic	
	exoskeleton	
Protocol Number	TBD	
Methodology	Within-subjects design	
Study Duration	10 months	
Study Center(s)	College of St. Scholastica, maurices Community Clinic	
Main Objective	Determine the effectiveness of the HWA to alter joint	
	kinematic and EMG magnitudes in individuals post-stroke	
Number of subjects	12	
Diagnosis and main criteria	Cerebrovascular accident (CVA), ≥12 weeks but <1 year post,	
	Age: 18-85 years, Walk 10 meters with stand by assistance	
	with or without orthosis or cane	
Study Product (s)	Honda Walking Assist (HWA) robotic exoskeleton	
Duration of administration	2 Testing sessions (~5-6 hours total across the 2 sessions)	
Reference condition	Walking without HWA	
Statistical Methodology	Paired t-tests, Multiple ANOVAs	

Background and rationale:

Background of the question and study rationale:

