Here we propose to quantify the effect of the HWA on walking at the knee, ankle, trunk and arm segments during phases of the gait cycle (GC) as described by Perry. (Perry & Davids, 1992) Additionally, we will quantify the aftereffect of HWA use in these joints and segments. Quantification will include measurement of walking kinematics (joint angles), muscle activity (EMG output), ground reaction forces and Spatiotemporal gait characteristics measured in three conditions: 1) Walking at self-selected pace (control), 2) walking with the HWA (4Nm assist), 3) and immediately following HWA walking (aftereffect). Our overall hypothesis is that walking with the HWA in the (hip flexion and extension) assist mode results in reallocation of cortical motor resources to the knee, ankle, trunk and arm. We also propose that normalizing walking through optimization (activation of latent residual capacity) of previously non-optimized corticospinal motor units with the HWA will produce a short-term (or within-session) aftereffect. We hypothesize that aftereffect will be greater in individuals with less lower extremity use since their stroke. Therefore we will characterize lower extremity use by quantifying the average number of steps each participant takes using an activity monitor.

Background of the device:

The Honda Walking Assist (HWA) System (pictured below) is a robotic device developed by Honda R&D Corporation ®, Japan (https://world.honda.com/Walking-Assist/). It is controlled through software run on a tablet. The device weights 2.7 kgs and has two brushless motors that run on a lithium ion battery with an approximate running time of 60 minutes. It comes in 2 sizes with adjustable frames making it possible to fit a variety of body types/sizes.

It takes approximately 5 minutes to fit the HWA on to the user. It's computer-activated motors use hip angle information to guide assistance delivered through the thigh straps to the legs in time with the walking cycle. The maximum torque delivered is 4 Nm. Wearers have described this level of assistance as "mild" to "moderate". The goal of device use is to promote walking ease by increasing stride length and improving the step symmetry.

Honda began leasing the HWA in Japan in 2015, in January of 2018 they obtained medical device approval in the European Union. Food and Drug administration approval of the HWA in the United States is in process at this time.

Study Objectives:

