Specific Aim I: Determine the effectiveness of the HWA to alter joint **kinematic** and **EMG** magnitudes at the knees and ankles in individuals post-stroke.

Sub Aim I- Determine the effect of HWA on paretic limb weight acceptance patterns. Specifically, knee flexion angle achieved at initial swing (62-75% GC) and EMG output at terminal swing and initial contact.

Hypothesis: In the HWA walking and after-assist condition, knee flexion angle will be increased at initial swing and will positively correlate with the magnitude and/or timing of EMG output of the hamstring at terminal swing and quadriceps at initial contact compared to the control (no SMA) condition.

Sub Aim II- Determine the effect of HWA on walking propulsion. For example: ankle plantar flexion angle and EMG output achieved at terminal stance to preswing phase (~50% GC) of the gait cycle.

Hypothesis: In the HWA walking and after-assist condition, peak plantarflexion angle will increase at terminal stance and will positively correlate with the magnitude and/or timing of EMG output of the medial gastrocnemius compared to the control condition.

Sub Aim III- Determine the effect of HWA on ankle dorsiflexion angle at midswing.

Hypothesis: In the HWA walking and after-assist condition, peak ankle dorsiflexion angle at midswing will increase and will positively correlate with the magnitude and/or timing of EMG output of the tibialis anterior compared to the control condition.

Note: Our ability to answer this sub aim will be dependent on the number of participants enrolled who are able to ambulate safely without ankle foot orthoses (AFO).

Sub Aim IV- Determine the effect of HWA on EMG magnitudes in the non-paretic hip, knee and ankle musculature.

Hypothesis: EMG magnitudes will be lower in the non-paretic limb muscles in the HWA walking condition compared to the same muscles in the control condition.

Specific Aim II: Determine the effectiveness of the HWA to improve arm and trunk **kinematics** in individuals post-stroke.

Sub Aim I- Determine the effect of the HWA on the Arm posture score for each limb.(Riad, Coleman, Lundh, & Broström, 2011)

Hypothesis: In the HWA walking and after-assist condition, an arm posture score that falls within normal parameters will be present in contrast to the control condition.

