- measure of sensitivity thought to reflect A α axon transmission. (Rolke et al., 2006) It will be quantified in seconds and scored using the average of three trials with a 128 Hz tuning fork placed on the skin at the base of the great toenail. (Janz, Bjorkland, Kramer, Oczak, & Borstad, 2018)
- 6. The StepWatch Activity Monitor will be used to characterize participants physical activity based on their daily step counts. Participants will wear StepWatch Activity Monitor on the less affected lower extremity during their daily routines for 8 hours per day for three days. Verbal and written instructions will be provided. The StepWatch is reliable and has been validated to provide the most accurate measurements of physical activity in persons with slow walking, such as may be caused by stroke. (Mudge, Stott, & Walt, 2007) (Mudge & Stott, 2008) Physical activity as measured by daily step count is a potentially large source of variability within the participants that will be important to characterize and understand. In Specific Aims 1 and 2 we will be attempting to quantify a differenced between the control condition and the aftereffect of walking with the HWA. Because we hypothesize that aftereffect will be greater in individuals with less lower extremity use (those who take fewer steps) since their stroke it is important to collect data on this variable.

Description of measures used to quantify effect of HWA on walking

- 7. Kinematic Analysis of Gait will be obtained using a Qualisys 8-camera motion capture system. Sample rate 120 Hz. A modified IOR gait marker set (~40 markers) applied bilaterally. (Cappozzo, Catani, Della Croce, & Leardini, 1995)
- 8. Analysis of muscle activation during gait using 16 Delsys Tringo EMG sensors applied over bilateral LE muscle groups including gluteus maximus (1), quadriceps (3), hamstrings (2), tibialis anterior (1), medial gastrocnemius (1), totaling 8 sensors per lower extremity. Sample rate 2000Hz
- 2 AMTI Force platforms will be used to quantify ground reaction forces (vertical load, horizontal shear, vector patterns, and center of pressure) for both lower limbs during gait. Sample rate 1200Hz.
- 10. Stair Climbing Ascent/Descent test- A timed test of the ability to ascend and descend stairs with our without a rail. For this study a flight of 7 stairs will be used. The means of two trials of ascending and descending will be recorded. (Flansbier et al., 2005)

Withdrawal or removal of participants from the study

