This study has a within-subjects design in which walking parameters including kinematics and muscle activity will be collected from participants during two testing sessions. For practical reasons a non-probability sample will be used. Pseudo randomization of participants into two groups will be used to control, in part, for the effect of order of testing on study outcomes.

Sample Size

The sample size for this study was calculated based on the assumption of detecting a meaningful difference in peak knee flexion angle (primary hypothesis) between the control and HWA walking conditions. To detect a mean difference of 5 degrees with a standard deviation of 5 degrees using a two-sided test and significance level of 5%, power of 80%, would require 10 participants. To allow for a 20% dropout rate 12 participants will be recruited. At the mid point of participant testing (6 participants) sample size will be recalculated and the sample adjusted if necessary to achieve appropriate power for the primary aims.

Data analysis plan

The measures collected for each subject in each condition will be compared within and across participants using paired t-tests and ANOVA. The alpha level will be set at p<0.05 to indicate statistical significance.

Data Management

Participant data collected in this study will be kept completely confidential and in compliance with HIPPA requirements. Participants will be assigned a study ID, all data collection forms and tools will use study ID therefore data will be de-identified. Data will be stored in locked cabinets, electronic data will be kept on secure, password protected computers. Data will be retained securely for three years after study publication.

References

- Botner, E. M., Miller, W. C., & Eng, J. J. (2005). Measurement properties of the Activities-specific Balance Confidence Scale among individuals with stroke. *Disability and rehabilitation*, 27(4), 156-163.
- Flansbjer, U.-B., Holmbäck, A. M., Downham, D., Patten, C., & Lexell, J. (2005). Reliability of gait performance tests in men and women with hemiparesis after stroke. *Journal of Rehabilitation Medicine*, *37*(2), 75-82.

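### Three Aim I hypotheses predict an angle–EMG correlation and another predicts a step-count effect, but the plan names only paired t-tests and ANOVA

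*Combined protocol and SAP*

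**What the plan says.** The document is a combined protocol and SAP. Its Data analysis plan gives the methods in one sentence, "The measures collected for each subject in each condition will be compared within and across participants using paired t-tests and ANOVA", followed by a 0.05 significance level. The Statistical Methodology row of the Study Summary agrees: "Paired t-tests, Multiple ANOVAs". No correlation coefficient, regression, covariate, step-count grouping or cut-off appears anywhere.

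Three hypotheses under Specific Aim I go beyond a difference in means, each for the HWA walking and after-assist conditions:

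- Sub Aim I: knee flexion at initial swing will rise and "will positively correlate with the magnitude and/or timing of EMG output of the hamstring at terminal swing and quadriceps at initial contact".
- Sub Aim II: "peak plantarflexion angle will increase at terminal stance and will positively correlate with the magnitude and/or timing of EMG output" (medial gastrocnemius).
- Sub Aim III: "peak ankle dorsiflexion angle at midswing will increase and will positively correlate with the magnitude and/or timing of EMG output" (tibialis anterior). A note makes this sub aim "dependent on the number of participants enrolled who are able to ambulate safely without ankle foot orthoses".

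A fourth hypothesis is in the background section: "We hypothesize that aftereffect will be greater in individuals with less lower extremity use since their stroke". Item 6 of the measures used to characterize participants (StepWatch) repeats it in terms of fewer steps and ties it to the outcomes: "In Specific Aims 1 and 2 we will be attempting to quantify a differenced between the control condition and the aftereffect". That item gives the hypothesis as a reason for collecting step data.

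**The concern.** A test of means can show that the angle rose and that EMG rose. It does not show whether the people whose angle rose more are those whose EMG rose more, which is what the three sub aims predict. Nor does it show how the aftereffect varies with daily steps.

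The text leaves further choices open. It allows EMG magnitude, timing or both. It does not say whether the correlation is across people within a condition or between changes from control. For step count it defines no factor, cut-off or covariate.

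If the plan is followed exactly, these hypotheses end untested. Otherwise they are tested with a method and an EMG variable chosen after the data have been seen.

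**Working it through.** **1. The plan's own figure.** Inputs from the Sample Size section: difference 5 degrees, SD 5 degrees, two-sided 5%, power 80%. Taking the SD as that of the paired difference, the standardized effect is 5/5 = 1. The noncentrality is 1 × √n on n − 1 degrees of freedom. Power is 0.748 at n = 9, 0.803 at n = 10 and 0.883 at n = 12. The stated 10 reproduces, and 10 × 1.2 = 12 gives the number recruited. This supports a mean difference in knee flexion and nothing else.

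**2. Can the named methods see a correlation?** Suppose each participant's full set of EMG values (control, HWA, after-assist) is reassigned to a different participant. Every paired t-test and every condition ANOVA on EMG is unchanged, and so is every one on angle. The angle–EMG correlation across participants, or across their change scores, can change completely. The named analyses therefore carry no information about it.

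**3. Step count by ANOVA or by regression.** The documents give no expected correlation, so r = 0.5 is assumed. Simulated power, two-sided 5% (200,000 replicates):

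| Analysis | n = 10 | n = 12 |
|---|---|---|
| Regression on continuous steps | 33% | 40% |
| Same, with a Group A/B term | 29% | 36% |
| Median-split ANOVA | 20% | 24% |

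A hand check of the last row: for normal data a median split multiplies the correlation by √(2/π) = 0.798, so 0.5 becomes 0.399. With Fisher's z, atanh(0.399) = 0.422. At n = 10, 0.422 × √7 − 1.96 = −0.84, which is 20% power. At n = 12, 0.422 × √9 − 1.96 = −0.69, which is 24%.

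**4. What a correlation can show at this size.** The smallest significant correlation is t/√(n − 2 + t²).

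- n = 10: 2.306/√(8 + 5.318) = 0.63.
- n = 12: 2.228/√(10 + 4.964) = 0.58.

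An observed r of 0.5 has a 95% interval of tanh(0.549 ± 1.96/√(n − 3)): −0.19 to 0.86 at n = 10 and −0.10 to 0.83 at n = 12. Power of a change-score correlation in one condition at a true r of 0.5 is 33% (n = 10) or 40% (n = 12). If Sub Aim III were left with 6 people, which is an assumption, it would be 17%.

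**5. Why the form of the correlation should be fixed in advance (illustration only).** Suppose the three conditions were pooled with participant terms but no condition term, and both angle and EMG shifted by 1 SD of the paired difference in the two HWA-related conditions, with no person-level association. The pooled correlation would be significant in 46% (n = 10) or 54% (n = 12) of trials. With a shift of 0.5 SD it is about 9% to 10%. With a condition term, and no person-to-person variation in response, it is about 5%. The 1 SD shift matches the planning value for knee angle; the EMG shift is an assumption.

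**6. Group order and step count.** Under the Testing Plan, StepWatch instruction is given on the first testing day and the monitor is collected at the second session. Group A has the stair session first and Group B the walking session. Steps are thus recorded after a session that differs by group. If the groups differed by an assumed 1 SD in both steps and aftereffect, with no true link, regression without a group term would be significant in 8.7% (n = 10) or 9.7% (n = 12) of trials, and in 5.0% with the term.

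**The case against.** The strongest reply is that the gap is small. The primary comparison is sound. The step-count hypothesis is in no numbered aim, and StepWatch is listed among measures that characterize participants. ANOVA across participants could include a step-count factor. With 10 to 12 people, any correlation will be imprecise whatever the plan says.

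Much of this stands. It is why the point is confined to secondary hypotheses and why an exploratory label is appropriate. It does not close the gap. The StepWatch item states the directional hypothesis, and the only groups defined, A and B, serve testing order. An ANOVA factor would still leave the three correlation hypotheses unaddressed. Those three belong to Specific Aim I, while the plan labels only Aim VI exploratory.

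Two stronger readings are tempting. A reader might infer that the freedom to choose EMG magnitude or timing inflates chance findings. The sub aims join HWA walking and after-assist with *and*. Requiring a positive result in both conditions gives chance success of 0.1% to 2.1% even with free choice, below the 2.5% for a single positive result at two-sided 5%. Sub Aim I also requires hamstring and quadriceps. A reader might also take the 46% to 54% above as this trial's error rate. That pooled analysis is nowhere in the plan and assumes an EMG shift the documents do not give. It also counts device-induced movement shared by angle and EMG as false, although the text could be read as meaning just that.

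**Conclusion.** The concern holds for the secondary hypotheses. Paired t-tests and ANOVA cannot estimate the angle–EMG correlations predicted in Sub Aims I to III. They could address step count only by grouping a continuous measure, at a cost of 13 points of power with 10 participants (33% − 20%) and 16 with 12 (40% − 24%). Those figures rest on an assumed correlation of 0.5 and a median split. The documents supply neither.

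The mean comparison of peak knee flexion and its sample size are not in question. The documents do not support a claim that the plan as written inflates false positives. The plan should be amended before EMG data are analysed, because the remedy is cheap and the open choices affect the answer.

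**What to change.** Add to the Data analysis plan:

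- **(a) Angle and EMG.** For each of Sub Aims I to III, name one EMG variable per muscle group (magnitude or timing) before EMG data are analysed. State how the three quadriceps and two hamstring sensors per leg are combined. Report the correlation between change in angle and change in EMG, with a 95% confidence interval, for HWA minus control and for after-assist minus control. Support requires both conditions and, for Sub Aim I, both hamstring and quadriceps. Any analysis that pools conditions includes participant and condition terms. For Sub Aim III, state the number analysed without an ankle foot orthosis.
- **(b) Step count.** Regress the aftereffect (post-HWA minus control) on continuous mean daily steps, with peak knee flexion as lead outcome. Report the slope with its 95% confidence interval. Repeat with a Group A/B term, because steps are recorded after a first session that differs by group.
- **(c) Status.** Label both analyses exploratory, because the sample was sized only for the mean difference in knee flexion.

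The cost is a little more analysis work on data already to be collected, and loss of the freedom to choose between EMG magnitude and timing. Power stays low: about 33% to 40% at r = 0.5 for each change-score or step-count estimate, and less where both conditions must agree. The intervals should therefore carry the interpretation.
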